5.22 Primary-assisted Patency

If a subject is a success on primary patency, then they are a success on primary-assisted patency and require no further evaluation via this algorithm. If a subject is a failure on primary patency without a subsequent TVR then they are a failure on primary-assisted patency and require no further evaluation via this algorithm. Subjects failing primary patency for a significant stenosis diagnosed via imaging and undergoing a TLR will be assessed following the TLR for primary-assisted patency by the algorithm below.

Unique composite endpoint such as primary-assisted patency contains both site-reported imaging endpoint and clinical/safety endpoint (by cut-off days), the event of the individual components will be determined first and the composite endpoint will then be determined as the following (apply to primary patency failure subjects following TLR for significant stenosis only):

Freedom from significant stenosis/occlusion within 1-Month	Freedom from 2 nd CD TLR within 37 Days	1-Month Primary-assisted Patency
Yes	Yes	Yes
Yes	No	No
Yes	Missing Data	Missing Data
No	Yes	No

Freedom from significant stenosis/occlusion within 1-Month	Freedom from 2 nd CD TLR within 37 Days	1-Month Primary-assisted Patency
No	No	No
No	Missing Data	No
Missing Data	Yes	Missing Data
Missing Data	No	No
Missing Data	Missing Data	Missing Data

Once a failure of primary-assisted patency has occurred in a subject by the algorithm above then all future time points reporting primary-assisted patency will be set to failure. If there are no failures and one or more successes, then the subject is a success up to the time of the last success recorded.

Primary-assisted patency at 6 months follow-up will be determined following similar convention specified above for 1 month.

5.23 Secondary Patency

If a subject is a success on primary patency, then they are a success on secondary patency and require no further evaluation via this algorithm. If a subject is a failure on primary patency without a subsequent TVR then they are a failure on secondary patency and require no further evaluation via this algorithm. Subjects failing primary patency and undergoing a TLR for total occlusion diagnosed via imaging will be assessed following the TLR for secondary patency by the algorithm below.

Unique composite endpoint such as secondary patency contains both site-reported imaging endpoint and clinical/safety endpoint (by cut-off days), the event of the individual components will be determined first and the composite endpoint will then be determined as the following (apply to primary patency failure subjects following TVR for total occlusion only):

Freedom from significant stenosis/occlusion within 1-Month	Freedom from 2 nd CD TLR within 37 Days	1-Month Secondary Patency
Yes	Yes	Yes
Yes	No	No
Yes	Missing Data	Missing Data
No	Yes	No
No	No	No
No	Missing Data	No

Freedom from significant stenosis/occlusion within 1-Month	Freedom from 2 nd CD TLR within 37 Days	1-Month Secondary Patency
Missing Data	Yes	Missing Data
Missing Data	No	No
Missing Data	Missing Data	Missing Data

Once a failure of secondary patency has occurred in a subject by the algorithm above then all future time points reporting secondary patency will be set to failure. If there are no failures and one or more successes, then the subject is a success up to the time of the last success recorded.

Secondary patency at 6 months follow-up will be determined following similar convention specified above for 1 month.

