5.2 Effectiveness Endpoints

Patency effectiveness endpoints (site-reported endpoints) include the endpoints that are determined by site assessment (DUS or angiography), such as the significant stenosis/occlusion measured by DUS or angiography as well as consideration of the clinical endpoint – TVR. Such site-reported endpoints rely on the actual evaluable assessment. If the scheduled assessment is not completed or the data is not evaluable (i.e., not readable, or non-diagnostic), it will be treated as missing value and will be excluded from the analysis.

The significant stenosis component for the patency endpoints (primary patency and primary-assisted patency) is determined by a qualified angiogram diameter stenosis (DS) $\geq 50\%$ and $<100\%$ evaluated by the site or qualified DUS evaluated as DUS category ‘50-99%’ that is evaluated by the site-reported DUS. The occluded component of primary and secondary patency endpoints is determined by a qualified angiogram DS=100% or qualified DUS evaluated as ‘occluded’. Either significant stenosis or occlusion will be considered failure of primary patency.

Data will be used for subjects who have an evaluable (readable or diagnostic) scheduled or unscheduled DUS or angiographic assessment (site-reported imaging assessments) that will be based on reporting windows described below. To minimize the missing assessment at 1 and 6-month visits, analysis windows provided below will be utilized.

Given that angiography is a more precise visualization of the vessel than DUS, in cases where both angiography and DUS are available at the same assessment and they provide different conclusions then angiography will be preferentially used in the algorithm.

Step 1. For convention, the imaging visits use the following reporting windows. The study day used in the window definitions is calculated as “assessment date” minus “Index procedure date”:

Study Visit	Target Day	Compliance Reporting Windows	Analysis Reporting Windows
Index Procedure	Day 0	N/A	N/A
Discharge	Discharge	N/A	1-discharge
30-days	Day 30	Study Day 23 – 37	15-60
6-month	Day 180	Study Day 166 – 194	61-210

These reporting windows serve 2 primary functions:

- 1) Allow for the calculation of compliance to imaging follow-up for each visit – compliance reporting window ranges.
- 2) Provide the analysis reporting windows for patency endpoints at key follow-up time points.

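### SAP 5.23 conflicts with 5.2 on what loses secondary patency and assigns no outcome to vessels re-treated for stenosis, so secondary patency can be reported below primary-assisted patency

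*SAP*

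**What the plan says.** The protocol lists secondary patency at 30 days and 6 months (section 7.5, item 10) without defining it, so the SAP holds the only operational definition.

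SAP 5.2 describes the imaging components. For stenosis: "The significant stenosis component for the patency endpoints (primary patency and primary-assisted patency) is determined by" a diameter stenosis of at least 50% and below 100%, or the 50-99% duplex category. For occlusion: "The occluded component of primary and secondary patency endpoints is determined by a qualified angiogram DS=100"% or a duplex reading of occluded. It adds: "Either significant stenosis or occlusion will be considered failure of primary patency".

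SAP 5.23 then sorts subjects into three groups:

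- Primary patency successes are secondary successes.
- For untreated failures, "If a subject is a failure on primary patency without a subsequent TVR then they are a failure on secondary patency".
- For re-treated failures, "Subjects failing primary patency and undergoing a TLR for total occlusion diagnosed via imaging will be assessed following the TLR for secondary patency". The table that follows is restricted again: "apply to primary patency failure subjects following TVR for total occlusion only". Its imaging column is headed "Freedom from significant stenosis/occlusion within 1-Month", and its second column is freedom from a second clinically driven TLR.

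SAP 5.22 has the same first two groups for primary-assisted patency. Its table takes only subjects re-treated for significant stenosis.

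**The concern.** There are two separate problems.

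(a) Section 5.2 does not list secondary patency among the endpoints that carry the stenosis component, but 5.23 lets stenosis cause failure in two places: the untreated-failure rule and the imaging column of the table. A programmer cannot follow both sections.

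(b) A subject re-treated for stenosis belongs to none of the three groups in 5.23. The subject is not a primary success, is not without a later TVR, and was not re-treated for occlusion. Section 5.22 does give this subject a primary-assisted outcome, which may be success.

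At stake is a listed secondary endpoint at two time points. It could be reported lower than the 5.2 rule implies, and below the primary-assisted figure. The result would also depend on how the programmer treats unassigned subjects, a choice that could be made after the data are seen.

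**Working it through.** The plan gives no patency rate, re-treatment rate or power for this endpoint, so there is no figure to reproduce. I traced each possible course through the rules. Here *patent* means free of stenosis, occlusion and a second clinically driven TLR.

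| Course | Primary-assisted (5.22) | Secondary (5.23) | Secondary, occlusion only (5.2) |
|---|---|---|---|
| Primary success | success | success | success |
| Stenosis, no TVR | failure | failure | success |
| Stenosis, TLR, then patent | success | none assigned | success |
| Stenosis, TLR, then stenosed but open | failure | none assigned | success |
| Stenosis, TLR, then occluded | failure | none assigned | failure |
| Occlusion, no TVR | failure | failure | failure |
| Occlusion, TLR, then patent | none assigned | success | success |
| Occlusion, TLR, then stenosed but open | none assigned | failure | success |
| Occlusion, TLR, then occluded | none assigned | failure | failure |

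**Which rule affects the order.** Let A be primary successes, Sr stenoses re-treated and then patent, Or occlusions re-treated and then patent, and N all subjects. With unassigned subjects counted as failures:

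- primary-assisted = (A + Sr)/N
- secondary = (A + Or)/N
- difference = (Sr − Or)/N

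The order reverses exactly when Sr exceeds Or. Untreated stenoses are in neither numerator, because 5.22 and 5.23 fail them alike.

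**Example 1** (assumed counts; N = 110 for scale): A = 90, untreated stenosis 8, Sr = 8, untreated occlusion 2, Or = 2.

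- Unassigned as failures: primary-assisted (90 + 8)/110 = 89.1%; secondary (90 + 2)/110 = 83.6%.
- Unassigned excluded: primary-assisted 98/(110 − 2) = 90.7%; secondary 92/(110 − 8) = 90.2%. Still reversed.
- Secondary under the 5.2 rule: (90 + 8 + 8 + 2)/110 = 108/110 = 98.2%. Of the 16 subjects lost under 5.23, 8 come from (a) and 8 from (b).

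**Example 2** (assumed): A = 92, untreated stenosis 8, Sr = 2, untreated occlusion 2, Or = 6. With unassigned as failures, primary-assisted is 94/110 = 85.5% and secondary is 98/110 = 89.1%. No reversal.

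**Example 3** (assumed): A = 88, untreated stenosis 8, Sr = 6, stenosis re-treated and stenosed again 2, untreated occlusion 2, Or = 3, occlusion re-treated and later stenosed but open 1. With unassigned as failures, 94/110 = 85.5% against 91/110 = 82.7%: reversed. With unassigned excluded, 94/106 = 88.7% against 91/102 = 89.2%: not reversed. The handling alone decides the order.

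**Repairing one part only.** With (b) repaired, secondary successes include A + Sr + Or, which is never below A + Sr. With only (a) repaired, the order can still reverse. Take assumed counts A = 90, untreated stenosis 6, Sr = 10, untreated occlusion 4: secondary is (90 + 6)/110 = 87.3% against primary-assisted 100/110 = 90.9%.

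**The mirror gap in 5.22.** Suppose 5.23 is repaired but 5.22 still leaves occlusion re-treatments unassigned and they are excluded. With 109 primary successes and one occlusion re-treated and then occluded again, primary-assisted is 109/109 = 100% and secondary is 109/110 = 99.1%. The two rates need the same denominator. On a common denominator, the repaired rule gave no reversal in any of 3456 assumed count combinations.

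**The case against.** The best counter-argument is that 5.2 only says how each component is measured and does not allocate components exhaustively. Read exhaustively, it would also remove occlusion from primary-assisted patency, yet the 5.22 table counts occlusion too. So 5.2 may be loosely worded, and the sponsor may have wanted a stricter secondary patency. Nor does either document state that the three measures must be ordered.

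Part of this stands: 5.2 fits 5.22 imperfectly, and the ordering is not written down. But if the stricter definition is intended, 5.2 has to change, because the sections cannot both be applied as they read. Both 5.22 and 5.23 carry primary successes forward, which shows that nesting is intended at least that far. The missing outcome in 5.23 does not depend on how 5.2 is read.

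A reader might infer that the rule for untreated failures is what puts secondary below primary-assisted patency. It is not: the same rule is in 5.22. A reader might also infer that 5.23 scores stenosis re-treatments as failures. It is silent on them; failure is one possible handling.

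**Conclusion.** The SAP is wrong as written on this endpoint. Part (a) lowers secondary patency relative to the 5.2 rule. Part (b) leaves a definable group without an outcome and allows secondary patency to fall below primary-assisted patency. The reversal is conditional: with unassigned subjects as failures it requires Sr to exceed Or, and with exclusion it depends on the denominators as well.

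The size cannot be estimated from the documents. Every count above is an assumption, and the gaps shown are not forecasts. It would also be too strong to call the endpoint uninterpretable: primary successes and untreated failures are scored explicitly, and only the re-treated subjects lack a complete rule. Secondary patency has no hypothesis or performance goal. The primary endpoints, sample size and success criteria (SAP 4.5) are untouched.

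**What to change.** Amend the SAP before the patency analysis is run:

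1. Reconcile 5.2 and 5.23: define loss of secondary patency as occlusion (diameter stenosis of 100%, or duplex occluded) not restored by re-intervention.
2. Carry primary-assisted successes forward as secondary successes.
3. Count open vessels with 50-99% stenosis as secondary-patent, whether or not re-treated.
4. Rename the imaging column of the 5.23 table *Freedom from occlusion*.
5. Remove or revise the second-TLR column in 5.23. Otherwise a vessel that is open after a second TLR still fails, against item 1.
6. Use either TLR or TVR throughout 5.23. The entry sentence says one and the table restriction the other, so a TVR that is not a TLR has no clear path.
7. State in 5.22 the primary-assisted outcome for subjects re-treated for occlusion, so that both rates use the same subjects.

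The cost is SAP wording and programming. The stenosis and occlusion categories are already defined in 5.2, so no new data are needed.

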5.24 Endpoint Assessed by Office Visit

Such endpoints include WIQ Scores, etc. These assessments /endpoints are obtained/determined through the office visit assessment. If the office visit is not completed then these assessments will not be available, and therefore will be treated as missing values and will excluded from the analysis.

For the assessments that are recorded on the scheduled visits forms, the scheduled visit number will be used in the analyses.

For subjects that don't have any assessment for a scheduled visit (visit not done or the visit is completed by the assessment is not readable), the following rules will be used to slot the unscheduled visit assessments:

- 1) Assessments will be slotted into each study visit (including scheduled and unscheduled visit) using the visit date, visit window is described in previous section;
- 2) The assessments with unevaluable values will be excluded from the visit slotting step;
- 3) If multiple assessments are slotted into the same visit window, the assessment with non-missing value that is closest to or earlier than the scheduled visit date will be used. If multiple non-missing assessments have equal distance from the scheduled visit date, the assessment from the earlier assessment will be used.
